5. STATISTICAL AND ANALYTICAL PLANS

5.1. Disposition of patients

Patient disposition will be based on all included patients (that is to say patients included in the study by having a questionnaire partly or fully filled in) and will display patients prematurely withdrawn of the study and reasons why patients were prematurely withdrawn.

Frequency of patients by centre within country and frequency of patients by visits will be tabulated. Amongst patients indicated as having undergone the follow-up, some were indicated as being prematurely withdrawn from the study. These patients had either no results collected at this visit or only one result (no suspicion of NSF), therefore it has been decided that the reliable data is the withdrawal form and so these patients were eventually considered as having not undergone the follow-up 3 visit.

Centre characteristics and radiological activities of centres will be tabulated.

A listing showing disposition of patients and a listing showing centre characteristics and radiological activities of centres will be provided in CSR appendix 16.2.1.

5.2. Data Sets Analysed and protocol deviations

Data sets analysed

There will be three patient populations defined for this study: all-included population (AIP), safety population (SP) and efficacy population (EP).

The all-included population (AIP) will include all patients who have a questionnaire partly or fully filled in. This population will be used for the description of disposition of patients, protocol deviations and demographic data.

The safety population (SP) will include all patients receiving at least one injection of contrast media regardless of the quantity. This population will be used to evaluate the NSF occurrence, to describe administration modalities, for analysis of adverse events, laboratory data, other safety observations, medical events and concomitant medications presentation. Furthermore, demographic data and medical history will be presented using this population as well.

The efficacy population (EP) will include all patients who have an available imaging assessment.

The following table describes how the above-defined patients populations will be used in the different analyses conducted.

CONFIDENTIAL	
FORM STATISTICAL ANALYSIS PLAN N° DGD-55-003 VERSION N° 2 DATED: 26 FEBRUARY 2018 (REF I011622)
	F015830-01 Page 14 / 49
--------------	---	----------------------------

Analysed populations

Analysed Populations	AIP	SP	EP
Population characteristics	✓(only Demographics)	✓	
Exposure		✓	
Efficacy assessment			✓
Safety assessment : Main criterion		✓	
Safety assessment : Secondary criteria (AE, laboratory data and other safety observation)		✓	
Concomitant medications		✓	

Frequency and percentages of patients in each population will be presented. A listing showing the distribution of each patient in the populations will also be provided in CSR appendix 16.2.3.

Protocol deviations

A protocol deviation is any change, divergence, or departure from the study design or procedures defined in the protocol that might significantly affect the completeness, accuracy, and/or reliability of the study data or that might significantly affect a patient's rights, safety, or well-being. Protocol deviations are to be displayed in the Clinical Study Report (CSR) as a metric of the feasibility and reliability of the study.

The list of protocol deviations is defined in this document but protocol deviations can be added during the Data Review Meeting (DRM). Protocol deviations will be extensively sought from, clinical database and monitoring files (if monitoring was required as per local regulation).

As no efficacy or safety subset are defined, no deviation will lead to exclusion from this subset and therefore deviations will not be split in major and non major deviations.

The deviations are listed in the table below:

Category	Description
Inclusion/Non-inclusion criteria not met	Patient not scheduled for a contrast enhanced MRI with DOTAREM® or who will not be followed up for his/her renal impairment by one of the site study co-investigators
	Patient having mild renal impairment (eGFR 60-89 mL/min/1.73 m ²) or normal renal function (eGFR>90 mL/min/1.73 m ²)
	Patient has received a GBCA other than DOTAREM® within the past 12 months prior to inclusion in this study
	Patient has experienced a previous hypersensitivity reaction to GBCA
Non respect of study schedule and procedures	Patient is not injected
	Follow-up 1 visit is not performed

CONFIDENTIAL	FORM STATISTICAL ANALYSIS PLAN N° DGD-55-003 VERSION N° 2 DATED: 26 FEBRUARY 2018 (REF I011622)	F015830-01 Page 15 / 49
--------------	---	----------------------------

	Follow-up 2 visit is not performed
	Follow-up 3 visit is not performed
	Follow-up 1 visit is not done between 3 and 12 months after the study drug administration
	Follow-up 2 visit is not done between 13 and 21 months after the study drug administration
	Follow-up 1 visit is not done between 22 and 27 months after the study drug administration
	The interval of at least 3 months was not respected between two follow-up visits.

No deviation will lead to exclusion from analyses in this safety study.

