- If there is any suspicion of NSF

In case of NSF suspicion, a biopsy could be decided by the medical team as a part of the normal patient follow-up in order to confirm or not the diagnosis of NSF. In such a situation, the biopsy results will be collected in a follow-up form.

If any case of suspicion/diagnosis of NSF, the physician in charge of the patient management will promptly inform the local Sponsor (local pharmacovigilance contact) using the dedicated “Suspect Adverse Reaction report” (F006031-See appendix).

Three follow up visits will have to be reported as described below respecting patients' usual follow-up visits:

[figure not shown]
- FUP1: a visit occurring between 3 and 12 months
- FUP2: a visit occurring between 13 and 21 months
- FUP3: a visit occurring between 22 and 27months

Please note that there should be at least 3 months difference between each Follow-up visit reported in order to avoid redundant visits.

If no information could be obtained during the first year after DOTAREM administration from the patient, the physician in charge of the follow-up will be requested to check the hospital/medical notes of the patient and complete a follow up visit form with the data from the hospital notes. This will be requested again during the second year after the DOTAREM administration for the second follow-up and for the last follow-up as well.

The electronic questionnaire for patients of the same centre will be accessible by all investigators of the centre by using personalized logins and passwords. The electronic data collection system also allows follow-up of the changes made by each user.

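### The SAP deviation table gives the 22 to 27 month window to Follow-up 1 instead of Follow-up 3, so the headline deviation count is uninformative and no listed row tests Follow-up 3 against its window

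*SAP*

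**What the plan says.** Protocol section 3.3 sets three consecutive windows after administration: first "FUP1: a visit occurring between 3 and 12 months", then "FUP2: a visit occurring between 13 and 21 months", and finally "FUP3: a visit occurring between 22 and 27months". It adds a spacing condition: "there should be at least 3 months difference between each Follow-up visit reported in order to avoid redundant visits".

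The deviation table in SAP section 5.2 turns this schedule into rules. It has one row for each visit not performed, including "Follow-up 3 visit is not performed", then three window rows:

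- The opening window row covers the first visit: "Follow-up 1 visit is not done between 3 and 12 months after the study drug administration".
- The next one covers the second visit: "Follow-up 2 visit is not done between 13 and 21 months after the study drug administration".
- The third returns to the first visit, where the third would be expected: "Follow-up 1 visit is not done between 22 and 27 months after the study drug administration".

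A last row covers the 3-month spacing. The table feeds Table 14.1.2.1, which has a row for patients with at least one deviation, a row per deviation and the number of included patients as denominator. It also feeds Listing 16.2.2.1. SAP section 5.2 says that deviations are reported to show how feasible and reliable the study was, that more can be added at the Data Review Meeting, and that none excludes a patient from analysis.

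**The concern.** The third window row names the wrong visit. Follow-up 1 is given two windows that cannot both be met, and Follow-up 3 is given none.

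Two things are at stake. First, the overall deviation count would no longer separate patients who kept to the schedule from those who did not. Second, the deviation table would not report third visits made outside 22 to 27 months. The primary objective is the incidence of NSF with patients followed for two years, so a reader will want to know how many two-year visits took place at about two years. Table 14.1.1.2 counts patients at each visit but has no timing rows. A Follow-up 3 window row in Table 14.1.2.1 would be the natural place to summarise this.

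**Working it through.** The plan states no figure to reproduce here. The check sets the rules side by side and then applies them to possible visit schedules.

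**Step 1: the windows compared (months after administration).**

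| Visit | Protocol 3.3 | SAP 5.2 window rows |
|---|---|---|
| Follow-up 1 | 3–12 | 3–12 and also 22–27 |
| Follow-up 2 | 13–21 | 13–21 |
| Follow-up 3 | 22–27 | none |

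**Step 2: can a Follow-up 1 visit satisfy both of its rows?** It would need a date t with 3 ≤ t ≤ 12 and 22 ≤ t ≤ 27. As 12 < 22, there is none. A visit at 3 to 12 months breaks the second rule, a visit at 22 to 27 months breaks the first, and any other date breaks both. A patient with no Follow-up 1 meets the row for that visit not being performed. Every included patient therefore has at least one deviation.

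**Step 3: schedules that fully comply with the protocol.** Take whole months, with window endpoints included and at least 3 months between consecutive visits. Count by month of Follow-up 2, as (allowed Follow-up 1 months) × (allowed Follow-up 3 months):

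- month 13: 8 × 6 = 48
- month 14: 9 × 6 = 54
- months 15 to 19: 5 × (10 × 6) = 300
- month 20: 10 × 5 = 50
- month 21: 10 × 4 = 40

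The total is 48 + 54 + 300 + 50 + 40 = 492. As written, 492 of 492 are flagged. With the third window row attached to Follow-up 3, 0 of 492 are flagged.

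**Step 4: schedules whose only fault is the timing of Follow-up 3.** Keep Follow-up 1 and Follow-up 2 in window and the spacing respected, and put Follow-up 3 at months 16 to 21 or 28 to 36. This gives 976 schedules. As written, none is flagged for Follow-up 3 timing; each is flagged, but for its correctly timed first visit. With the row corrected, all 976 are flagged for the Follow-up 3 window.

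**Step 5: what the spacing rule catches.** With Follow-up 2 in window and Follow-up 3 later but no later than month 21, there are 8 + 7 + 6 + 5 + 4 + 3 + 2 + 1 = 36 whole-month pairs. The gap is 1 or 2 months in 8 + 7 = 15 of them, so the rule catches 15 of 36, and only because the visits are too close together. For a late visit, the smallest gap is 28 − 21 = 7 months, so the rule catches none.

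These are counts of possible schedules on an assumed grid. They are not forecasts of patient numbers.

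**The case against.** The strongest reply is that this is an evident copying slip that would correct itself. The window rows run in time order, the rows before them run through visits 1, 2 and 3, and the protocol leaves one workable reading. SAP section 5.2 defines a deviation as a departure from what the protocol sets out, and a first visit at 3 to 12 months is not one. A literal program would flag almost every first visit, which would be hard to miss, and SAP section 3.1 plans quality control. It probably is a slip. But SAP section 3.1 also says that the analysis is carried out on the basis of this document, and the row is an operative rule. The Data Review Meeting is described as able to add deviations; adding a Follow-up 3 row would leave the false Follow-up 1 row in place.

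A second reply concerns reach, and it stands. A reader might infer that the timing of the two-year visit is never checked, or that this row is the only check on two-year observation. The documents do not support either. The spacing rule applies to Follow-up 3, and its absence is a listed deviation. Table 14.1.1.1 reports withdrawals with reasons, Table 14.1.1.2 reports attendance at Follow-up 3, and Listing 16.2.1.1 prints the visit dates patient by patient. What is missing is narrower: a listed row that tests Follow-up 3 against its window.

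**Conclusion.** The SAP row contradicts the protocol and is wrong as written. Applied literally, it makes the count of patients with at least one deviation 100% of included patients and leaves Follow-up 3 visits outside 22 to 27 months uncounted as such. This rests on three assumptions: the row is programmed verbatim, follow-up visits carry usable dates, and the not-performed row is applied to every included patient without a first visit, whatever the reason.

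A reader might go further and infer that the NSF estimate is at risk. It is not. SAP section 5.2 excludes nobody for a deviation, and the primary summary in SAP section 5.6.2 counts suspicions and diagnoses in the safety population with no visit-window condition. Numerator, denominator and populations are the same whichever visit the row names. The damage is confined to Table 14.1.2.1 and Listing 16.2.2.1. The row should be corrected because it is a working rule and the correction is plain, not because any safety result depends on it.

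**What to change.** Reconcile the row with protocol section 3.3: in "Follow-up 1 visit is not done between 22 and 27 months after the study drug administration", replace visit 1 with visit 3 and leave the rest unchanged. Replace the row; do not add a second one beside it. Then confirm that the deviation program tests Follow-up 1 only against 3 to 12 months and Follow-up 3 against 22 to 27 months, and that Table 14.1.2.1 and Listing 16.2.2.1 follow from it.

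The cost is one character in the SAP and about one line of code. No new data are needed, because the visit dates are already collected for Listing 16.2.1.1.

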5.3. Measurements of study drug compliance

None

5.4. Demographic and Other Baseline Characteristics

All demographic variables and other baseline characteristics will be presented using the SP. Demographics variables will be presented using the AIP as well.

Demography

Summary statistics for quantitative variable will be calculated for age, body weight, height and BMI. Frequency and percentages will be calculated for gender.

BMI will be derived for each collection of body weight using the formula: $BMI = \frac{\text{BodyWeight_Kg}}{\text{Height_m}^2}$

Magnetic Field

Summary statistics for qualitative variable will be presented for magnetic field (in tesla).

Current renal status

Summary statistics for quantitative variable will be calculated for serum creatinine, estimated creatinine clearance and eGFR. Frequency and percentages will be calculated for current renal status.

Serum creatinine will be presented in $\mu\text{mol/L}$. Therefore, conversion will apply for measurement in mg/L and mg/dL using the following conversion factors [1]:

From mg/dL to $\mu\text{mol/L}$: multiply by 88.4

From mg/L to $\mu\text{mol/L}$: multiply by 8.84

Should be noted that an aberrant result of serum creatinine was entered in the database for one patient ($1.36 \mu\text{mol/L}$). As it was impossible to correct this discrepancy in the database, it was decided not to present it in the statistical results of the clinical study report.

CONFIDENTIAL	FORM STATISTICAL ANALYSIS PLAN N° DGD-55-003 VERSION N° 2 (REF I011622)	F015830-01 Page 16 / 49
--------------	--	----------------------------

The estimated creatinine clearance (mL/min) will be calculated using the Schwartz formula for children less than 2 years old. The eGFR (mL/min/1.73 m²) will be calculated using the MDRD formula otherwise. They will be presented independently.

Risk factors

Frequency and percentages will be calculated for each risk factor. Specification for other cardiovascular disease, nervous system disorders, other treatments at risk and dose of Erythropoietin will be only listed.

Previous examination with GBCA

Number of patients with at least one previous examination with GBCA will be displayed globally and by classified name of product. Name of product will be classified as the following:

- If the words “Gadovist” or “Gadavist” appear in the product name then class= “Gadobutrol”
- If the word “Dotarem” appears in the product name then class= “Gadoterate meglumine”
- If the word “Primovist” or “Gd-EOB-DTPA” or “Gd EOB” appear in the product name then class= “Gadotexate disodium”
- If the words “Magnevist” or “Gadopentetate” appear in the product name then class= “Gadopentetate dimeglumine”
- If the word “Multihance” appears in the product name then class= “Gadobenic acid meglumine”
- If the word “Omniscan” appears in the product name then class= “Gadodiamide”
- If the word “Optimark” appears in the product name then class= “Gadoversetamide”
- If the words “No contrast” or “without contrast” or “NA” or “Non-contrast brain MRI” appear in the product name then class = “Without Contrast”
- If the words “Unknown” or “MD” or “UN” or nothing appear in the product name then class = “Missing”
- Otherwise then class= “Other”

Recent surgeries

Surgeries done less than two years before the MRI examination with DOTAREM® will be only listed. Number of patients with at least one surgery will be tabulated.

Concomitant treatments

Concomitant treatments at the time of the MRI examination with DOTAREM® will only be listed. Number of patients with at least one concomitant medication will be tabulated.

Indication of MRI examination

Indication of MRI examination will be tabulated by main classification (Central nervous system, whole body, musculoskeletal system, angiography and other) and sub classification.

Some indications for MRI categorized as “Other” should be classified in pre-defined categories according to the following algorithm:

If the wording contains “angio” or “anjio” then classify to Angiography system and according to the following for the sub classification:

If the wording is:	Specified Organ
“kidney” or “kidneys” or “renal” or contains one of these	2=Renal

CONFIDENTIAL	
FORM STATISTICAL ANALYSIS PLAN N° DGD-55-003 VERSION N° 2 DATED: 26 FEBRUARY 2018 (REF I011622)
	F015830-01 Page 17 / 49
--------------	---	----------------------------

“iliac” or contains “iliac”	3=Aorto iliac
“calf”	4=Calf
“Otherwise”	5=Other

Otherwise classify to whole body system and according to the following, for the sub classification:

If the wording is:	Specified Organ
“liver” or contains “lilver”	1=Liver
“kidney” or “kidneys” or “renal” or contains one of these	2=Kidney
“pancreas”	3=Pancreas
“pelvis” or contains “pelvic” or contains “pelvin”	4=Pelvis
“lung”	5=Lung
“heart” or “cardiac” or “cardio”	6=Heart
“breast”	7=Breast

Premedication

Patients having received at least one premedication will be presented. Premedication received will be only listed.

Listings of all demographic parameters and baseline characteristics will be presented in CSR Appendix 16.2.4.

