### ***3.2 Study population***

Over a twenty-month period, each participating radiological site will include in this study patients (adults and children), who have moderate (eGFR 30-59 ml/min/1.73m^2) to severe (eGFR<30 ml/min/1.73m^2) and end stage (eGFR<15 ml/min/1.73m^2) renal impairment or dialysis, scheduled for a contrast enhanced MRI with DOTAREM®. A patient will not be included in case of contra-indication to MR examination or for any other criteria as defined below and in the product SPC (Summary of Product Characteristics) corresponding to the marketing authorization in each of the involved countries.

Patients will be included in the study following the criteria detailed below:

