### ***3.3 Data collection***

Each patient will be identified by a unique number in the study.

At the time of inclusion, some demographic and patient medical and biological history information will be collected by the radiological team on a dedicated electronic case report form.

These data will include the most recent available serum creatinine level and ionograms level (calcium, phosphates ...)

The estimated Glomerular Filtration Rate (eGFR) (MDRD formula for adults) or estimated creatinine clearance (eCrCl) (Schwartz formula for children) will be calculated and reported on the form as well.

MDRD formula : (for adults only)

$$\text{eGFR (ml/min/1.73m}^2\text{)} = 186 \times \text{Cr}^{-1.154} \times \text{age}^{-0.203} \times k$$

where :       $k = 1$  for males

$k = 0.742$  for females

$k = 1.212$  for black patients

                  Cr = creatinine (mg/dl)

                  age (years)

Schwartz formula : (for children only)

$$\text{eCrCl (ml/min)} = [k \times \text{height}] / \text{Cr}$$

where :       $k = 29$  for newborns

$k = 40$  for infants

$k = 49$  for children < 12 years old

$k = 53$  for girls (12-18 years old)

$k = 62$  for boys (12-18 years old)

                  height (cm)

                  Cr = creatinine ( $\mu\text{mol/l}$ )

The indication for the MRI examination will be specified on this form as well as data relative to DOTAREM® administration (volume, type of injection, number of injections, nature and volume of package used). The product will be administered under conditions strictly in accordance with the local product SPC.

Image and diagnostic quality will be assessed by the radiologist.

The Adverse Events (AE) occurring during the MRI examination or during the time of usual follow-up post DOTAREM® administration will be notified and described.

In any case of Serious Adverse Event (SAE), the radiologist will promptly inform the local Sponsor (local pharmacovigilance contact) using a dedicated "Suspect Adverse Reaction report" (F006031-See appendix)

All patients will be followed up during 2 years after DOTAREM® administration to collect data on any suspected NSF or NSF related symptoms. When the patient visits his/her physician for routine follow-up, a follow up study form will be completed by the physician in the electronic case report form. The physician will have to report:

- If any medical events have occurred since the last visit of the patient,
- If a renal function assessment has been done

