2. EVALUATION CRITERIA

2.1. Demographic and other baseline characteristics

Demographic variables collected for this study are:

- Age in years for patient more than 2 years old and age in months otherwise,
- height,
- weight,
- sex.

Baseline characteristics collected for this study are:

- Magnetic field,
- Current renal status according to the investigator,
- Most recent serum creatinine before inclusion (in mg/L or mg/dL or μ mol/L),
- Estimated creatinine clearance for children less than 2 years old and eGFR otherwise,
- Pre-existing risk factors and medical history,
- Previous examinations with GBCA,
- Concomitant treatment and recent surgery (<2 years),
- Indication of MRI examination,
- Premedication.

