	Male	xxx (xx.x%)
	Female	xxx (xx.x%)
	Missing (if applicable)	xx
Age (years) for Patients Older than Two Years Old	n	XXX
	Mean (SD)	xx.x (xx.x)
	Median	xx
	Min ; Max	xx ; xx
	Missing (if applicable)	xx
Age (month) for Patients Younger than Two Years Old	n	XXX
	Mean (SD)	xx.x (xx.x)
	Median	xx
	Min ; Max	xx ; xx
	Missing (if applicable)	xx
Weight (kg)	n	XXX
	Mean (SD)	xx.x (xx.x)
	Median	xx
	Min ; Max	xx ; xx
	Missing (if applicable)	xx
Height (cm)	n	XXX
	Mean (SD)	xx.x (xx.x)
	Median	xx

CONFIDENTIAL	FORM STATISTICAL ANALYSIS PLAN N° DGD-55-003 VERSION N° 2 DATED: 26 FEBRUARY 2018 (REF I011622)	F015830-01 Page 29 / 49
--------------	---	----------------------------

Total (N=XXX)		
Min ; Max	xx ; xx	
Missing (if applicable)	xx	
Body Mass Index (kg/m ²)	n	xxx
	Mean (SD)	xx.xx (xx.xx)
	Median	xx.x
	Min ; Max	xx.x ; xx.x
	Missing (if applicable)	xx
Body Mass Index by Class	n	xxx
	< 18.5 kg/m ²	xxx (xx.x%)
	≥ 18.5 and < 25 kg/m ²	xxx (xx.x%)
	≥ 25 and < 30 kg/m ²	xxx (xx.x%)
	≥ 30 kg/m ²	xxx (xx.x%)
	Missing (if applicable)	xx

SD: Standard Deviation.

%: (n row / n non missing) * 100.

Source: Listing 16.2.4.1.

Table 14.1.4.1.2 Demographic Characteristics – Safety Population

Same as table 14.1.4.1.2

Table 14.1.4.2 Magnetic Field - Safety Population

Total (N=XXX)		
Magnetic Field (Tesla)	n	xxx
	1.5	xxx (xx.x%)
	3	xxx (xx.x%)
	Missing (if applicable)	xx

%: (n row / n non missing) * 100.

Source: Listing 16.2.4.2.

Table 14.1.4.3 Current Renal Status - Safety Population

Total (N=XXX)		
Intensity of Impaired Renal Function	n	xxx
	Moderate	xxx (xx.x%)
	Severe	xxx (xx.x%)
	End Stage Renal Insufficiency or Dialysis	xxx (xx.x%)

CONFIDENTIAL	FORM STATISTICAL ANALYSIS PLAN N° DGD-55-003 VERSION N° 2 DATED: 26 FEBRUARY 2018 (REF I011622)	F015830-01 Page 30 / 49
--------------	--	----------------------------

		Total (N=XXX)
	Kidney Transplantation	xxx (xx.x%)
	Missing (if applicable)	xx
If End Stage Renal Insufficiency or Dialysis, Specify	n	xxx
	Hemodialysis	xxx (xx.x%)
	Peritoneal Dialysis	xxx (xx.x%)
	Missing (if applicable)	xx
Most Recent Serum Creatinine (μmol/L)	n	xxx
	Mean (SD)	xx.xx (xx.xx)
	Median	xx.x
	Min ; Max	xx.x ; xx.x
	Missing (if applicable)	xx
Estimated Creatinine Clearance (mL/min) for Patients Younger than 2 Years Old		xxx (xx.x%)
If Yes, Estimated	n	xx
	Mean (SD)	xx.xx (xx.xx)
	Median	xx.x
	Min ; Max	xx.x ; xx.x
	Missing (if applicable)	xx

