eGFR (mL/min/1.73 m ²) for Patients Older than 2 Years Old		xxx (xx.x%)
If Yes, eGFR	n	xx
	Mean (SD)	xx.xx (xx.xx)
	Median	xx.x
	Min ; Max	xx.x ; xx.x
	Missing (if applicable)	xx

eGFR: Estimated Glomerular Filtration Rate.

SD: Standard Deviation.

%: (n row / n non missing) * 100, except for Estimated Creatinine Clearance and eGFR variables %: (n row / N safety population) * 100.

Source: Listing 16.2.4.3.

CONFIDENTIAL	FORM STATISTICAL ANALYSIS PLAN N° DGD-55-003 VERSION N° 2 DATED: 26 FEBRUARY 2018 (REF I011622)	F015830-01 Page 31 / 49
--------------	---	----------------------------

Table 14.1.4.4 Pre-existing Risk Factor and Medical History - Safety Population

	Total (N=XXX)
Liver Disorder	xxx (xx.x%)
Allergies	xxx (xx.x%)
Previous Reaction to Contrast Agents	xxx (xx.x%)
GBCA	xxx (xx.x%)
Iodinated Contrast Agent	xxx (xx.x%)
Bronchial Asthma	xxx (xx.x%)
Hypertension	xxx (xx.x%)
Heart Insufficiency	xxx (xx.x%)
NYHA Class I	xxx (xx.x%)
NYHA Class II	xxx (xx.x%)
NYHA Class III	xxx (xx.x%)
NYHA Class IV	xxx (xx.x%)
Other Cardiovascular Disease	xxx (xx.x%)
Diabetes Mellitus	xxx (xx.x%)
Type I	xxx (xx.x%)
Type II	xxx (xx.x%)
Proteinuria	xxx (xx.x%)
Nervous System Disorders	xxx (xx.x%)
At Risk Treatments	xxx (xx.x%)
Beta-Blockers	xxx (xx.x%)
Interleukine2	xxx (xx.x%)
Other	xxx (xx.x%)
Hypothyroidism	xxx (xx.x%)
History of Deep Venous Thrombosis	xxx (xx.x%)
Erythropoietin	xxx (xx.x%)
Acidosis	xxx (xx.x%)
Hyperphosphatemia	xxx (xx.x%)
Abnormal Ca ⁺⁺ Level	xxx (xx.x%)
High Serum Ferritin Level	xxx (xx.x%)

GBCA: Gadolinium based Contrast Agent ; NYHA: New York Heart Classification.

%: (n row / N safety population) * 100.

Source: Listing 16.2.4.4.

Table 14.1.4.5 Previous Examinations with GBCA - Safety Population

	Total (N=XXX)
Previous Examination	n xxx
Yes	xxx (xx.x%)
No	xxx (xx.x%)

CONFIDENTIAL	FORM STATISTICAL ANALYSIS PLAN N° DGD-55-003 VERSION N° 2 DATED: 26 FEBRUARY 2018 (REF I011622)	F015830-01 Page 32 / 49
--------------	--	----------------------------

Total (N=XXX)		
	Missing (if applicable)	xx
If Yes*	Gadobutrol	xxx (xx.x%)
	Gadoterate Meglumine	xxx (xx.x%)

	Without Contrast	xxx (xx.x%)
	Missing	xxx (xx.x%)

GBCA: Gadolinium based Contrast Agent.

%: (n row / n non missing) * 100, except for multiple answers %: (n row / n with previous examination) * 100.

*As multiple examinations with various GBCA are possible, the sum of percentage could be greater than 100.

Source: Listing 16.2.4.5.

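### The SAP uses Schwartz only below age 2 and MDRD for everyone else, while the protocol limits MDRD to adults; SAP section 4 does not record the change

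*SAP*

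**What the plan says.** Protocol 3.2 enrols "patients (adults and children". Protocol 3.3 then gives two formulas divided by age group. The first is headed "MDRD formula : (for adults only", and Schwartz is marked as being for children only. The Schwartz constants are 29 for newborns, 40 for infants, 49 for children under 12, 53 "for girls (12-18 years old" and 62 for boys of the same ages. The site calculates the estimate and enters it on the case report form.

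The SAP divides patients at a different age, and does so consistently:

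- SAP 5.4: creatinine clearance "will be calculated using the Schwartz formula for children less than 2 years old", while eGFR "will be calculated using the MDRD formula otherwise".
- SAP 2.1, among the baseline characteristics: "Estimated creatinine clearance for children less than 2 years old and eGFR otherwise".
- SAP 7.2, shell of Table 14.1.4.3: one row is "Estimated Creatinine Clearance (mL/min) for Patients Younger than 2 Years Old" and the other is eGFR "for Patients Older than 2 Years Old".

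SAP section 4 lists the changes to conduct and analysis: the lower minimum share of severe patients, the longer recruitment and early stop, the admission of patients with recent DOTAREM, and the dropping of statistical tests. It says nothing about the renal formula or its age limit.

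**The concern.** Moderate to severe renal impairment defines this study's population, and Table 14.1.4.3 with Listing 16.2.4.3 is where a reader checks who was studied. Under the SAP rule the Schwartz constants for ages 12-18 are never used, the under-12 constant is not applied from age 2 to 11, and MDRD is used where the protocol rules it out.

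For a child aged 2 to 17 this has three consequences:

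- The calculated value does not follow the protocol and is counted in the eGFR row instead of the creatinine clearance row.
- The value can disagree with the investigator's severity class in the same table.
- SAP 5.2 counts mild impairment or normal function (eGFR 60 or above) as an inclusion deviation, but does not say whether this is read from the site's estimate or the recalculated one. If from the recalculated one, an eligible child could be reported as wrongly enrolled, or a real deviation could be missed.

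**Working it through.** **Is the protocol rule current?** The supplied protocol already carries the global amendment: Protocol 3 has the 40% minimum for severe impairment, and the non-inclusion criteria allow earlier DOTAREM. It still limits MDRD to adults, so that amendment does not explain the split.

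**Inputs.** The formulas and constants are from Protocol 3.3. The conversion of 88.4 µmol/L per mg/dL is from SAP 5.4. Heights and creatinine values are assumptions, because the documents give no patient data. The documents state no figure on this point, so there is none to reproduce.

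- MDRD = 186 × (Cr/88.4)^-1.154 × age^-0.203 × k, with Cr in µmol/L and k = 1 (male) or 0.742 (female). The protocol's factor of 1.212 for black patients is left out; it would multiply the MDRD value and the ratio by 1.212.
- Schwartz = k × height (cm) / Cr (µmol/L), with k = 49 (under 12), 53 (girls 12-18) or 62 (boys 12-18).

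Worked example, boy of 3, 95 cm, 150 µmol/L:

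- MDRD = 186 × (1.697)^-1.154 × 3^-0.203 = 186 × 0.5432 × 0.8001 = 80.8.
- Schwartz = 49 × 95 / 150 = 31.0.
- Ratio = 80.8 / 31.0 = 2.61.

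| Assumed patient | SAP rule (MDRD) | Protocol rule (Schwartz) | Ratio |
|---|---|---|---|
| Boy 3, 95 cm, 150 µmol/L | 80.8 | 31.0 | 2.61 |
| Boy 5, 110 cm, 200 µmol/L | 52.3 | 26.9 | 1.94 |
| Boy 10, 140 cm, 150 µmol/L | 63.3 | 45.7 | 1.38 |
| Girl 10, 140 cm, 150 µmol/L | 47.0 | 45.7 | 1.03 |
| Girl 15, 162 cm, 250 µmol/L | 24.0 | 34.3 | 0.70 |
| Boy 17, 175 cm, 250 µmol/L | 31.5 | 43.4 | 0.73 |

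**Range of the ratio.** Both sexes, creatinine of 100, 150, 200, 300, 400 and 600 µmol/L, keeping cases with Schwartz below 60:

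| Age | Assumed heights (cm) | MDRD / Schwartz |
|---|---|---|
| 2 | 82-92 | 1.75-3.49 |
| 5 | 103-116 | 1.15-2.31 |
| 10 | 130-147 | 0.79-1.49 |
| 15 | 155-178 | 0.56-0.87 |
| 17 | 155-183 | 0.53-0.85 |

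The lowest value comes from an extreme case, a girl of 17 at 183 cm and 600 µmol/L. At 163 cm her ratio is 0.59.

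**Crossing the deviation limit of 60.** A boy of 5 (110 cm, 120 µmol/L) has MDRD 94.3 and Schwartz 44.9, so the SAP formula would flag him and the protocol formula would not. A boy of 15 (168 cm, 150 µmol/L) has 58.3 and 69.4, the reverse. The protocol's Schwartz result is in ml/min and the bands are per 1.73 m², with no conversion given, so these comparisons are approximate.

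**Effect on the mean in the eGFR row.** Let a share p of the patients in that row be children, and assume an adult mean of 35. The mean moves by p × (child's MDRD − 35), compared with a row of adults only.

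- Children like the boy of 3: 0.01 × 45.8 = 0.46 and 0.05 × 45.8 = 2.29.
- Children like the girl of 15: 0.01 × (−11.0) = −0.11 and 0.05 × (−11.0) = −0.55.
- No children: 0.

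**The case against.** The best counter-argument is about weight. The value feeds one descriptive baseline table and its listing. The SAP plans no tests, no subgroups and no analysis by renal status, and follow-up laboratory output is serum creatinine only. The severity class is the investigator's, and no deviation removes anyone from analysis. The number of patients aged 2 to 17 is not given and may be zero. All of this stands, and it limits the importance of the point without removing the contradiction.

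Secondly, the split may mirror the patient questionnaire, which was not supplied, so some tabulated values could be those the site recorded. That is possible, but SAP 5.4 says the values will be calculated. If the split was deliberate, it needs a stated reason.

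Thirdly, section 4 refers to the amendments for the full list of changes, and those for Turkey and the United States were not supplied. A country amendment would not by itself support a rule the SAP applies to all patients.

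Lastly, the documents give no measured renal function to show which formula is nearer the truth. They support only the statement that the SAP value departs from the protocol's formula.

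**Conclusion.** The concern holds. The SAP assigns MDRD to ages at which the protocol excludes it, consistently across SAP 2.1, SAP 5.4 and Table 14.1.4.3, and section 4 does not disclose this. For an affected child the departure is often large: about 1.75 to 3.5 times the protocol value at age 2, and 0.53 to 0.85 times at age 17. Because the direction changes with age, no single correction factor would repair it. These sizes rest on assumed heights and creatinine values, and comparison with the renal bands rests on reading ml/min against ml/min/1.73 m².

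The consequence is confined to the calculated renal values in Table 14.1.4.3 and Listing 16.2.4.3, and possibly to the count of renal-function deviations. With no child aged 2 to 17 in the data, nothing changes. The SAP should still be corrected, since it must be right for every patient the protocol admits.

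**What to change.** 1. In SAP 2.1, SAP 5.4 and both row labels of Table 14.1.4.3, use Schwartz with the protocol's constants for all children and MDRD for adults only. Keep the two presented separately, each with its unit.
2. State which formula applies at age 18, because the protocol's bracket of 12-18 leaves this open.
3. In SAP 5.2, say that the renal-function deviation uses the protocol-based estimate, either as recorded by the site or recalculated with the protocol's formula. Say also how a Schwartz value in ml/min is compared with bands in ml/min/1.73 m².
4. Leave the severity category as the investigator's classification.
5. If the 2-year split is intended, record it with its reason in SAP section 4. Reporting the number of patients aged 2 to 17 would show whether it matters.

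The cost is SAP wording, two row labels and a small programming change. Age, sex, height and creatinine are already collected.
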